8.2 Adverse Events (AEs) and Serious Adverse Events (SAEs)

Study participants will be monitored for adverse events (AEs) during livestreaming classes by Moving Together coaches. Prior to the first class, instructors will create a list of class participants that is easily accessible and includes their names, phone numbers, addresses, emergency contact information, and local 10-digit emergency center number in case of potential AEs during class. If there is an emergency, the instructor will stop class, contact the Community Support Coordinator/PI, and call the local emergency center.

In addition, we will elicit information about AEs including falls and healthcare utilization in all study participants during monthly check-ins. All AEs will be tracked in a research study database that will include:

- Dyad PIDN
- Person affected (PWML or CG)
- Date of occurrence
- Date of first awareness
- Brief description of AE
- Initial determination of whether the event was study-related (definitely, possibly, unrelated)
- Initial determination of whether the event was serious or unexpected (yes/no)
- Whether the event is reportable (yes/no)
- If yes:
 - Date reported to SO
 - Date reported to NIA PO
 - Date reported to UCSF IRB
- Comments

Definitions are provided below.

Adverse event (AE):

Any negative medical occurrence in a research study participant that is temporally associated with their participation in the research, whether or not considered related to participation in the research.

Serious adverse events (SAEs):

Any AE that:

- Results in death
- Is life-threatening, or places the participant at immediate risk of death from the event as it occurred
- Requires or prolongs hospitalization
- Causes persistent or significant disability or incapacity
- Requires medical or surgical intervention to prevent an outcome listed above
- Changes the risk/benefit ratio

Unanticipated Problems (UPs):

- Unexpected, in terms of nature, severity, or frequency given (a) the research procedures described in the study protocol and informed consent documents and (b) the characteristics of the study population
- Definitely or possibly related to participation in the research
- Suggests that the research places participants or others at a greater risk of harm (including physical, psychological, economic, or social harm) than was previously known or recognized

Definitely Related: An AE is definitely related to study participation if it is clear that the event was caused by study participation. A definitely related event has a strong temporal relationship, and an alternative cause is unlikely.

Possibly Related: An AE is possibly related when there is a reasonable possibility that the event might have been caused by study participation or there is uncertainty about the relationship. For example, the AE may have a strong temporal relationship, but a potential alternative cause may be present. In other circumstances, there may be significant uncertainty about the cause of the event, or a possible relationship to study participation cannot reasonably be ruled out.

Unrelated: The cause of the AE is known, and the event is in no way related to any aspect of study participation. If there is any uncertainty regarding AE causality, then the event should be assessed as possibly related to research participation. Often, the cause of an unrelated AE is disease progression.

8.3 Reporting Procedures

All AEs that are both serious (SAE) and unexpected (regardless of whether they are related or not) will be reported to the NIA Program Officer (PO), the Safety Officer (SO), and the Institutional Review Board (IRB) at the University of California, San Francisco (UCSF) within 48 hours of awareness.

A summary of all other SAEs will be reported to the NIA PO and SO every six months based on the recommendations of the SO, given the relatively low risk of this study.

Because the study population includes older adults (many in their 80s or 90s) with dementia and other underlying health conditions, expected SAEs include:

- Death due to underlying health condition
- Life-threatening event due to underlying health condition
- Hospitalization for underlying health condition or illnesses unrelated to the study (such as infectious diseases)
- Decline in physical or cognitive function consistent with disease progression

8.4 Follow-up for Adverse Events

Unresolved AEs will be followed until resolved or considered stable. The Moving Together intervention team will follow up during subsequent contact until the AE is resolved for participants in the intervention.

8.5 Safety Monitoring

[name] (UCSF PI) and [name] (Together Senior Health PI) will be responsible for overseeing participant safety on a daily basis. [name] will be responsible for tracking AEs, SAEs and UPs and for preparing reports for the UCSF IRB, NIA PO and SO. The SO will act in an advisory capacity to the NIA PO to monitor participant safety and evaluate the progress of the study.

8.6 Protocol Violations and Research-Related Incidents

The University of California, San Francisco (UCSF) Institutional Review Board (IRB) is serving as the IRB of record for this study. Consistent with current UCSF guidelines, we will track all protocol violations and research-related incidents.

Protocol Violations: Any unapproved changes, departures or deviations from the study design or procedures of the research project that are under the investigator's control and have not been reviewed and approved by the IRB.

Major (Reportable) Protocol Violations: Any protocol violations that affect the participant's rights, safety, or well-being, or the completeness, accuracy and reliability of the study data. Criteria for defining major violations including any of the following:

- The violation has harmed, or posed a significant or substantive risk of harm, to the research participant.
- The violation resulted in a change to the participant's clinical or emotional condition or status.
- The violation has damaged the completeness or soundness of the data collected for the study.
- The violation is evidence of willful or knowing misconduct on the part of the investigator(s).
- The violation involves serious or continuing non-compliance with federal, state or local guidelines.

Minor (Non-Reportable) Protocol Deviations: Any protocol violations that do not have a major impact on participant's rights, safety, or well-being or the completeness, accuracy, and reliability of the study data. For example:

- A study participant skips a question on a survey, and the research team fails to check the survey for completeness.

Major (Reportable) Incidents: Any problematic or unanticipated events involving the conduct of the study or study participants that affect the rights, safety, or well-being of participants or others, or the completeness, accuracy and reliability of the study data. Examples include:

- Significant complaint or concern received from a potential or enrolled study participant.
- Inappropriate behavior of study participants and/or research personnel.
- Problems during study recruitment or the informed consent process.
- Problems with the study design in which a majority of participants have difficulty adhering to the study schedule of procedures.
- Potential breach of study participant's privacy or confidentiality (must be reported within 48 hours of PI awareness).
- Withdrawal or significant reduction in resources necessary to safely and adequately conduct study activities.

- Changes to the protocol to eliminate or reduce an apparent immediate hazard to the safety research participants or others.

Minor (Non-Reportable) Incidents: Any events involving the conduct of the study or study participants that are not problematic and do not involve significant potential to harm participants or others. Example:

- Receipt of a minor complaint from a study participant that is resolved by the research team.

Reporting of Protocol Violations and Research-Related Incidents

- All major protocol violations and major incidents will be reported to the UCSF IRB within 10 working days, and a copy of the report will be sent immediately to the NIA PO, and SO.
- Any breach of study participant's privacy or confidentiality will be reported to the UCSF IRB within 48 hours, and a copy of the report will be sent immediately to the NIA PO, and SO.
- All minor protocol violations and minor incidents will be tracked in the research database and available for review by the NIA PO, and SO if requested.

9 INTERVENTION DISCONTINUATION

Study participants may withdraw voluntarily from participation in the study at any time and for any reason. Participants will continue to be followed, with their permission, even if the study intervention is discontinued. Follow-up assessment visits will continue to be scheduled if the participant is agreeable. If not, we will follow-up via phone calls, letters, emails, text messages and/or medical record review, as allowed by the participants.

10 STATISTICAL CONSIDERATIONS

10.1 General Design Issues

The primary outcomes in people living with memory loss and caregivers will be self-rated quality of life using validated measures. Secondary outcomes in PWML will include change in mobility, well-being, social isolation and cognitive function. In CGs, secondary outcomes will include CG-rated self-efficacy, burden, social isolation, self-regulation, positive affect, and sleep as well as sleep, mobility, and cognitive function in PWML. Our hypotheses include the following:

1. We hypothesize that participation in Moving Together results in improved quality of life for PWML primarily through the domains of physical function (mobility), emotional well-being, social relationships (reduced social isolation) and cognitive function.
2. In CGs, we hypothesize that improved quality of life will be due to the changes observed in their loved ones (improved mobility, well-being, isolation, cognitive function, sleep) as well as changes in themselves (improved self-efficacy, reduced burden, reduced social isolation, improved self-regulation, increased positive affect, and improved sleep).

10.2 Sample Size and Power

To be conservative, power estimates were based on an unpaired t-test analysis with two-sided alpha=0.05. A sample size of 224 (112/group) will provide us with 80% power to detect a clinically meaningful standardized effect size of 0.375 to test Hypothesis 1a.

Assuming 20% attrition, we would have 80% power to detect a standardized effect size

of 0.395. For hypothesis 1b, we will be able to conduct exploratory analyses using the full sample of 224, since both groups will receive the intervention and will be offered the opportunity to participate in maintenance classes. Again assuming 20% attrition, a final sample of 179 will provide 80% power to detect correlation coefficients as small as 0.20.

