Our research suggests that these programs are associated with participant- and caregiver-reported improvements in quality of life including psychological well-being (happiness, enjoyment, relaxation); physical function (mobility, posture); social connection (engagement); and cognitive function (memory, awareness).^{8,9,15} However, some caregivers have reported increased burden associated with the logistics of having to bring persons with dementia to the in-person classes.¹⁵

During our Phase I SBIR grant, we applied human-centered design principles¹⁶⁻¹⁸ to

develop and pilot an online version of Paired PLIÉ called Moving Together. We successfully delivered the 12-week Moving Together program using a livestreaming virtual group class format to 21 people (11 persons with ADRD/MCI and 10 caregivers/study partners) in their homes. Of the 21 participants, 15 (70%) successfully completed the program, all of whom reported being highly satisfied with livestreaming virtual class delivery. When asked what they enjoyed most about the program, participants described physical, social and emotional benefits and also highlighted the benefits of being able to participate from home.

[figure not shown]
After completing the Phase I pilot, we have continued offering online Moving Together classes to ‘graduates’ of our online program as well as ‘naïve’ participants, including several new classes that were offered in response to COVID-19. As of June 2020, we have offered 164 classes that have included 52 unique individuals (30 people living with memory loss or MCI, 22 caregivers).

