6 RANDOMIZATION AND BLINDING

6.1 Randomization

Study participants will be enrolled in cohorts (blocks) of 16 dyads and randomly allocated to the immediate start intervention group ($n=8/\text{cohort}$) or the delayed start control group ($n=8/\text{cohort}$). The randomization sequence will be generated in advance by the data manager using a random number generator on a computer and will be stored separately and securely. Research staff will be unaware of the randomization sequence.

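### The detectable effect of 0.395 after 20% attrition does not follow from the plan's own inputs; it should be about 0.42, and the detectable correlation about 0.21

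*Combined protocol and SAP*

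**What the plan says.** All the inputs are in Section 10.2 (Sample Size and Power).

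- **Method:** "power estimates were based on an unpaired t-test analysis with two-sided alpha=0.05", chosen to be conservative.
- **Without attrition:** "A sample size of 224 (112/group) will provide us with 80% power" for a standardized effect of 0.375, which the protocol regards as clinically meaningful.
- **With attrition, hypothesis 1a:** "Assuming 20% attrition, we would have 80% power to detect a standardized effect size", and the value given there is 0.395.
- **With attrition, hypothesis 1b:** the 20% rate is applied again, and "a final sample of 179 will provide 80% power to detect correlation coefficients as small as 0.20".

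Section 6.1 confirms equal allocation, 8 and 8 dyads in each cohort of 16. Section 10.2 gives no correlation between repeated measures, no variance-reduction factor and no other attrition rate.

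**The concern.** For a two-group comparison of means, the detectable effect grows with one over the square root of the sample size. Losing 20% of the sample should therefore raise it by a factor of 1/√0.8 = 1.118, or about 12%. The plan raises it from 0.375 to 0.395, about 5%. That is the increase expected from losing about 10%.

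This is the plan's only power statement for the primary hypothesis that allows for dropout. As written, it makes 20% attrition look nearly free. The funder, the Safety Officer or a later reader would credit the design with more sensitivity than its stated assumptions give. They would not see that, on the stated basis, the type II error at 0.375 is near 30% rather than 20%.

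**Working it through.** **Inputs (Section 10.2):** unpaired t-test, two-sided alpha 0.05, power 80%, 224 dyads at 112 per group, 20% attrition, 179 dyads remaining. Check: 224 × 0.8 = 179.2, or about 89.5 per group.

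**Formula.** In the normal approximation, the detectable effect is d = (1.960 + 0.842) × √(2/n), with n per group. The exact figures use the noncentral t distribution.

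**Step 1: reproduce the no-attrition figure.** With n = 112, d = 2.802 × √(2/112) = 0.374 (normal) or 0.376 (t). Power at 0.375 is 80.1% (normal) or 79.8% (t). The stated 0.375 reproduces, which confirms the method.

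**Step 2: apply 20% attrition.** With n = 89.5, d = 2.802 × √(2/89.5) = 0.419 (normal) or 0.421 (t). Rounding to 89 or 90 per group gives 0.422 or 0.420 (t). The stated 0.395 does not reproduce.

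**Step 3: power at 179 dyads.**

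| Standardized effect | Power (t) | Power (normal) |
|---|---|---|
| 0.375 | 70.4% | 70.8% |
| 0.395 | 74.8% | 75.3% |
| 0.42 | 79.8% | 80.2% |

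**Step 4: what 0.395 requires.** It needs 101.6 per group (t) or 101 (normal). The implied attrition is 1 − 101.6/112 = 9.3%. As a cross-check, 0.375/√0.9 = 0.395, whereas 0.375/√0.8 = 0.419. To keep both 0.395 and 20% attrition, enrolment would have to be 2 × 101.6/0.8 = 254 dyads.

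**Step 5: other readings.**

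- A one-sided test at 0.05 with 89.5 per group gives 0.373.
- 20% loss in one arm only (112 against 90) gives 0.399, and would leave 202 dyads rather than 179.
- The normal approximation gives 0.419.

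None of these gives 0.395 at 20% attrition.

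**Step 6: the correlation.** By Fisher's z, the smallest detectable correlation is r = tanh(2.802/√(n − 3)).

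- With n = 179, r = tanh(2.802/√176) = 0.208.
- Power at r = 0.20 is Φ(0.2027 × √176 − 1.960) = Φ(0.729) = 76.7%.
- The n needed for r = 0.20 is (2.802/0.2027)² + 3, or about 194.
- A bias-corrected Fisher z gives 76.9% power and a minimum r of 0.208; a noncentral t version gives 77.5% and 0.206.

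**The case against.** The strongest reply is that the t-test is only a conservative stand-in. Section 10.3 plans a linear mixed model that includes everyone randomized and uses baseline and repeated measures, so actual power may exceed these figures. That is fair, and the 74.8% and 70.4% should be read as t-test powers, not as the power of the trial. As an illustration (the documents give no correlation), 80% power at 0.395 with 179 dyads would be restored by a baseline-to-follow-up correlation of about 0.35 if the model behaves like an analysis of covariance: 1 − r² = (0.395/0.421)² = 0.880. If it behaves like a comparison of change scores, the correlation needed is about 0.56: 2(1 − r) = 0.880. But Section 10.2 ties 0.395 to the t-test and states no such gain, so this does not make the printed figure right.

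Three further points stand as limits.

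- What a null result excludes depends on its confidence interval, not on the planned detectable effect. With 179 dyads the 95% half-width under the t-test is about 0.295 SD, whatever Section 10.2 prints. The harm is a misstated design sensitivity, not a wrong interval.
- The correlation gap is small and concerns analyses the protocol calls exploratory.
- The Phase I result ("Of the 21 participants, 15 (70%) successfully completed the program") cannot be used to argue for a higher attrition rate here. It counts individuals rather than dyads, and it measures programme completion, whereas Section 9 keeps following participants who stop the intervention. Nothing here relies on it.

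**Conclusion.** The concern holds. With the test, alpha, power, sample size and attrition that Section 10.2 states, the effect detectable after attrition is about 0.42, not 0.395. The difference is 0.026 SD, or about 5 percentage points of power at 0.395. At 0.375, power falls to about 70%. The correlation figure should be about 0.21 rather than 0.20, a minor error of about 3 points of power.

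The result assumes equal loss in the two arms and the unpaired t-test named in the plan; it needs no outside figure. A 10% attrition rate would account for 0.395, but that is an inference, because the documents do not say where the number came from. The enrolment target of 224 is paired with 0.375 before attrition, which reproduces, so it is not undermined by this error.

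**What to change.** Correct Section 10.2 so that effect size, attrition rate and sample size agree. Because both 20% and 179 are stated, the natural correction is to give a detectable standardized effect of 0.42 at 80% power with 179 dyads, to add that power at 0.375 is then about 70%, and to change the detectable correlation to 0.21. If 0.395 was meant to reflect a lower attrition rate, state that rate (about 9 to 10%), justify it, and replace the 179 to match. If the sponsor wants to claim the efficiency of the mixed model, give the assumed correlation between visits and base the calculation on that model.

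The cost of the natural correction is a change of text and slightly less favourable figures. Enrolment, endpoints and the analysis model do not change. Additional enrolment (to about 254 dyads) would arise only if the sponsor wished to keep 80% power at 0.395 under the t-test with 20% attrition.

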10.3 Data Analyses

We will examine distributions of all variables to assess for missingness, outlier values or skewed distributions using standard techniques (e.g., means, medians, standard deviations, ranges, tables, graphical techniques). We will assess balance between the immediate and delayed start groups by comparing baseline characteristics (e.g., means \pm SD, N [%]). If meaningful differences occur by chance, we will perform sensitivity analyses adjusting for these differences.

Our primary analytic approach will be linear mixed models (LMMs) with terms included for group, time, and group*time interaction with random intercepts and slopes. This approach will enable efficient estimation of change in primary outcomes over time while including all participants randomized (intent-to-treat) and accounting for baseline values and correlations between repeated measures over time. Milestone 1a will determine if there is a significant group*time interaction for our primary outcome of quality of life, with separate analyses performed for PWML and CGs. Milestone 1b will involve exploratory analyses to examine potential mechanisms of action. These will include using PROCESS to assess for indirect effects (mediation) and contingent effects (moderation) based on baseline characteristics of our study participants (e.g., age, sex, caregiving relationship) and changes in secondary outcomes (e.g., mobility, well-being, isolation). Exploratory analyses also will examine the impact of 'dose' (based on class attendance), and sensitivity analyses will be restricted to those with high compliance ($\geq 75\%$ class attendance). For covariates that have more than 10% missing data, we will consider using multiple imputation.

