8.5	Safety Monitoring	27
8.6	Protocol Violations and Research-Related Incidents	27
9	INTERVENTION DISCONTINUATION	28
10	STATISTICAL CONSIDERATIONS	28
10.1	General Design Issues	28
10.2	Sample Size and Power	28
10.3	Data Analyses	29
10.4	Interim Analyses and Stopping Rules	29
11	DATA COLLECTION AND QUALITY ASSURANCE	29
11.1	Data Collection Forms	29
11.2	Data Management	29
11.3	Quality Assurance	30
11.3.1	Training	30
11.3.2	Monitoring	31
12	PARTICIPANT RIGHTS AND CONFIDENTIALITY	31
12.1	Institutional Review Board (IRB) Review	31
12.2	Informed Consent Forms	31
12.3	Participant Confidentiality	31
12.4	Study Discontinuation	32
13	INTELLECTUAL PROPERTY AND DATA SHARING	32
13.1	Cooperative Research and Development Agreement (CRADA)	32
13.2	Material Transfer Agreement (MTA)	32
14	PUBLICATION OF RESEARCH FINDINGS	32
15	REFERENCES	32

PRÉCIS

Study Title

Extending Independence and Quality of Life for People with Alzheimer’s Disease or Dementia through Telehealth Program Delivery

Objectives

The primary goals of this Phase II Small Business Innovation Research (SBIR) grant are to: 1) determine whether livestreaming virtual group delivery of the Moving Together program improves quality of life in people living with mild Alzheimer’s disease and related disorders (ADRD) and caregivers, including exploration of potential mechanisms of action; 2) refine the platform for people with mild cognitive impairment (MCI) to expand the target audience; and 3) develop an instructor training program to meet the needs of a larger client base. **This study protocol focuses on Aim 1 only.**

Design and Outcomes

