4 SELECTION AND ENROLLMENT OF PARTICIPANTS

4.1 Inclusion Criteria

Participants must meet all the inclusion criteria to participate in this study.

Persons With Memory Loss (PWML):

- English language fluency;
- Reside in U.S.
- Diagnosis of mild cognitive impairment (MCI), Alzheimer's disease or other dementia
- Mild severity, assessed using the Quick Dementia Rating System (scores of 2.5 to 12.5)

Caregivers (CGs):

- English language fluency;
- Reside in U.S.
- caregiver for PWML;
- own one or more devices that can be used to participate in two-way livestreaming video classes (e.g., smart phone/tablet + TV, laptop or desktop with webcam, smart TV);
- willing and able to participate in two-way livestreaming group movement classes with PWML.

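### The primary model leaves out the randomisation cohort and the screening severity score, and any further covariates are chosen after an undefined check for imbalance; both should be prespecified in a form that affects the tested contrast

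*Combined protocol and SAP*

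**What the plan says.** Section 10.3 (Data Analyses) specifies a linear mixed model with group, time and group-by-time terms and random intercepts and slopes. It is said to account for baseline values and for correlation between repeated measures. The primary test is the interaction, run separately for persons with memory loss and for caregivers. No other covariate is named for this model. Baseline characteristics are compared between arms, and then: "If meaningful differences occur by chance, we will perform sensitivity analyses adjusting for these differences". The section does not say what counts as meaningful or which variables are candidates. It mentions multiple imputation for covariates with more than 10% missing data, without naming any covariates. Age, sex and caregiving relationship appear only as example moderators in the exploratory Milestone 1b.

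Two baseline variables come with the design. Section 6.1 states "Study participants will be enrolled in cohorts (blocks) of 16 dyads", split 8:8 within each; Section 3 gives 14 such cohorts. Section 4.1 requires "Mild severity, assessed using the Quick Dementia Rating System (scores of 2.5 to 12.5", so severity is scored before randomisation. Section 4.1 also requires a diagnosis of mild cognitive impairment (MCI), Alzheimer's disease or another dementia.

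**The concern.** Covariates chosen because they look unbalanced are chosen for the wrong reason. What matters for precision is whether a variable predicts the outcome, not whether it happens to differ between arms. Because the plan gives neither a threshold nor a list, an adjusted result of unknown content may appear beside the primary one, and a reader could not tell whether another reasonable choice would have given a different answer.

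Two natural candidates are meanwhile left out. Cohort is the unit within which dyads were allocated, so an analysis that ignores it does not follow the randomisation. Severity spans a wide range and may well predict how quality of life changes over 12 weeks. At stake are some precision, a standard error that matches the blocked design, and a clear rule for adjustment.

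**Working it through.** **Inputs.** From Section 10.2: "power estimates were based on an unpaired t-test analysis with two-sided alpha=0.05"; 112 per arm, 80% power, standardised effect 0.375; 179 dyads (about 89.5 per arm) after 20% attrition. From Sections 3 and 6.1: 14 cohorts of 16, split 8:8. Not in the documents, so assumed: the extra share of variance, R², that QDRS and cohort explain beyond the baseline outcome. I take 0 to 0.10. I read the tested contrast as the change from V1 to V2.

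**Step 1: the plan's own figure.** Plan: "A sample size of 224 (112/group) will provide us with 80% power to detect a clinically meaningful standardized effect size of 0.375". The normal approximation gives n = 112 per arm and power 80.1%. The noncentral t gives power 79.8% and a detectable effect of 0.376. The figure reproduces, and it assumes no covariate adjustment, so the sample size does not depend on adjustment. With 179 dyads the same method gives 0.421. The plan states 0.395 at that attrition, which does not reproduce; that is a separate matter, and I use 0.421 here.

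**Step 2: do covariates entered as main effects help?** Let x be severity, γ the cohort effect and u the person effect.
- V1: Y₁ = a + βx + γ + u + e₁
- V2: Y₂ = a + βx + γ + u + τ + δ·group + e₂
- Change: Y₂ − Y₁ = τ + δ·group + (e₂ − e₁)

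The terms βx and γ cancel. With complete data the estimate of δ and its standard error are the same with or without them.

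**Step 3: what does a severity-by-time term add?** If severity also predicts change, with slope θ per SD, the variance of change contains θ², and a severity-by-time term removes it. Illustration, with all values assumed: person variance 0.6, visit variance 0.4, θ = 0.2 in size.
- Without the term: SE = √[(2 × 0.4 + 0.2²) × 2/112] = √(0.84/56) = 0.1225
- With the term: SE = √(0.80/56) = 0.1195, lower by 1 − √(0.80/0.84) = 2.4%

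A simulation with 14 blocks of 16 and two visits (severity slope 0.4 on level, cohort SD 0.2) agrees:

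| Mean SE of group-by-time | No covariates | Main effects only | Plus severity-by-time |
|---|---|---|---|
| Complete data | 0.123 | 0.123 | 0.120 |
| 20% dropout | 0.1341 | 0.1338 | 0.1309 |

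**Step 4: general size if the covariates act on the tested contrast.** The SE and the detectable effect are multiplied by √(1 − R²).

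| Assumed extra R² | SE reduction | Detectable effect, 112/arm | Power at 0.375, 112/arm | Detectable effect, 179 dyads |
|---|---|---|---|---|
| 0 | 0% | 0.376 | 79.8% | 0.421 |
| 0.02 | 1.0% | 0.372 | 80.6% | 0.417 |
| 0.05 | 2.5% | 0.366 | 81.8% | 0.410 |
| 0.10 | 5.1% | 0.357 | 83.8% | 0.399 |

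The starting values are those of an unadjusted t-test, which the plan itself calls conservative. The table therefore shows the proportional gain, not the power of the mixed model.

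**Step 5: cohort.** Arms are balanced 8:8 in every cohort, so with complete data cohort cannot bias the comparison. Including it mainly brings the reported SE into line with the design, and it matters only as far as cohorts differ in change or, in a baseline-adjusted model, in the 12-week value given baseline.

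**The case against.** The primary analysis is fixed in advance and ranked above the sensitivity analyses. A reader might infer that the primary test is picked after looking at the data. Section 10.3 does not support that, because the imbalance rule reaches only sensitivity analyses. Section 6.2 also keeps the statistician blind to which arm is which, which limits any steering. Both points stand. They leave the content of the adjusted analysis undefined.

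Three further inferences go beyond the documents.
- *That adding covariates is equivalent to many more dyads.* For the planned interaction this fails: main effects cancel (Step 2). Any gain needs terms that act on change, and an R² that the documents do not give and that could be zero.
- *That diagnosis is known for everyone.* The list of protocol changes (Section 16) records that V1.4 did not require a diagnosis and that V1.6 restored the requirement. Dyads enrolled in between may lack one, and the documents do not say how many there are. The same list says that severity was still scored with the QDRS under V1.4.
- *That adjusting for severity would tie the result to mild Alzheimer's disease and related disorders.* The précis names that group in its first goal and mentions MCI in its second: "refine the platform for people with mild cognitive impairment (MCI) to expand the target audience". But a severity term still yields one pooled effect; only an interaction or subgroup estimate would be specific to a group. Section 1.1 states the objective for people with memory loss, and exploratory moderation by baseline characteristics is already planned with an open list.

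It is also fair to say that QDRS describes the person with memory loss, so its value for the caregiver SF-12 is unknown.

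**Conclusion.** The point holds as a worthwhile, low-cost improvement. It is not a flaw that invalidates the primary test. Apart from the baseline outcome, no covariate is prespecified, the cohort used for randomisation is not in the model, and the rule for further adjustment is undefined and depends on the data.

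The precision at stake is modest and conditional: an SE reduction of 0 to 5.1% for an assumed extra R² of 0 to 0.10, and about 2% in the illustration with severity-by-time. It is nil for the complete-data interaction if the covariates enter only as main effects. I am confident about the missing specification and much less so about the size of the gain, which rests wholly on assumed variances.

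**What to change.** In Section 10.3, replace the imbalance trigger with a fixed covariate set for the primary model: screening QDRS score (continuous) and randomisation cohort. State one of two forms.

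1. The mixed model, with QDRS-by-time and cohort-by-time terms.
2. A baseline-adjusted (ANCOVA-type) comparison of the 12-week value at V2, with group, baseline outcome, QDRS and cohort. The baseline outcome is then used once, as a covariate and not also as a response.

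Keep the model without QDRS and cohort as the sensitivity analysis, and apply the set whatever imbalance is seen. Add diagnosis (MCI versus dementia) only after confirming that it is recorded for all randomised dyads. Say whether the same set applies to the caregiver SF-12 model. Optionally, report the effect by severity or by diagnosis as a secondary estimate.

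The cost is a change of wording, made before outcome data are examined by arm, plus a check that the numerical QDRS score, and not only a pass, was kept for each dyad. Cohort as a fixed effect uses about 13 degrees of freedom (14 − 1), or about 26 if cohort-by-time terms are added, out of 224 dyads; a random cohort effect uses fewer.
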